6.5 Missing Data Imputation

No global imputation is taking place at the database level. Efficacy and safety related imputations, as applicable, are outlined in Section 10.1 and Section 11.1, respectively.

6.6 Rounding of Numeric Results

Rounding will be performed for presentation of results. No rounding will be performed before or during analyses.

The mean and median will be rounded for presentation to 1 decimal more than the data were entered into the database. The standard deviation will be rounded to 2 decimal

places more than the data that were entered into the database. The minimum and maximum values will be presented as entered into the database.

Probabilities will be rounded to 3 decimal places before assignment of statistical significance and will be presented in rounded format. Probabilities that round to zero or are reported by SAS as zero will be presented as "< 0.001."

7.0 Demographics, Baseline Characteristics, Medical History, and Previous/Concomitant Medications

7.1 Demographic and Baseline Characteristics

All demographic and baseline variables will be described with summary statistics. Categorical data will be summarized using the frequency and percentage; continuous data will be summarized using the mean, standard deviation, median, first quartile, third quartile, minimum, and maximum. The number of non-missing values will also be summarized.

All summaries will be presented for the ITT Population. No statistical tests will be performed.

The following demographic and baseline parameters will be summarized.

Demographic

- Sex [male, female]
- Age [years]
- Age category [< 40, 40 – 64, ≥ 65]
- Body weight [kg] – overall and by gender
- Height [cm]
- Body mass index [kg/m²]
- BMI Category [< 25 , 25 – < 30, ≥ 30]
- Race
- Ethnicity

Tobacco/Nicotine and Alcohol Use

- Tobacco/Nicotine Use [current, former, never, unknown]
- Alcohol Use [current, former, never, unknown]

Baseline Characteristics

- Duration of Ps: The duration of Ps will be calculated relative to the date of screening visit (i.e., duration = [date of screening visit – date of onset] + 1. Duration of Ps will be expressed in years, by dividing the result in days by 365.25.
- Psoriatic arthritis (PsA) status [yes, no]
- Duration of Psoriatic arthritis (PsA): The duration of PsA will be calculated relative to the date of screening visit (i.e., duration = [date of screening visit – date of onset] + 1. Duration of PsA will be expressed in years, by dividing the result in days by 365.25.
- Family history of psoriasis [yes, no]

Baseline Characteristics – Efficacy Assessments

- Psoriasis Area and Severity Index (PASI)
- Physician's Global Assessment of Skin Psoriasis (PGA-S)
- Dermatology Life Quality Index (DLQI)
- Body Surface Area affected by Psoriasis (BSA)
- Satisfaction Questionnaire – Investigator
- Satisfaction Questionnaire – Subject
- Hi-sensitivity C-reactive Protein (hs-CRP)

Vital Signs

- Systolic blood pressure (mmHg)
- Diastolic blood pressure (mmHg)
- Pulse (bpm)

- Respiratory rate (rpm)
- Body temperature (°C)
- ECG (Normal, Abnormal – not clinically significant, Abnormal – clinically significant, Unable to evaluate)

Chest X-Ray, TB Test and BCG Vaccination History

- Chest x-ray (Normal, Abnormal, Missing)
- Calcified granulomas (Absent, Present, Missing)
- Pleural scarring (Absent, Present, Missing)
- Pleural thickening (Absent, Present, Missing)
- Signs of active TB (No, Yes, Missing)
- PPD TB test (< 5 mm, \geq 5 mm, missing)
- Quantiferon TB test (Negative, Indeterminate, Positive, Missing)
- Enrolled on TB Prophylaxis (No, Yes, Missing)
- TB History – at higher risk (No, Yes, Missing)
- BCG immunization (No, Yes, Unknown)
- Active or latent TB (No, Yes, Missing)

The following variables will be presented in listing format:

- Physical Examination
- Pregnancy Test

7.2 Medical History

Medical history will be summarized using body systems and condition/diagnosis as captured on the eCRF. The body systems will be presented in alphabetical order and the conditions/diagnoses will be presented in alphabetical order within each body system. The number and percentage of subjects with a particular condition/diagnosis will be summarized. Subjects reporting more than one condition/diagnosis within a body system will be counted only once for that body system.

7.3**Prior Treatment and Concomitant Medications**

The number and percent of subjects who received a prior or concomitant medication will be tabulated by the generic name assigned by the World Health Organization (WHO) Dictionary.

A prior medication is defined as any medication taken prior to the maximum date of either the first dose of study ADA or the first dose of MTX during the study. A concomitant medication is defined as any medication that started prior to the aforementioned date and continued to be taken after the maximum date of either the first dose of study ADA or the first dose of MTX or any medication that started on or after the date of the first dose of study drug, but not after the last study ADA dose date during the study.

Prior Ps treatment received and discontinued (including reason for discontinuation) prior to screening will be summarized as well.

7.4**Protocol Deviation**

Number and percentage of subjects who reported at least 1 of the following protocol deviation categories will be provided:

- Inclusion/exclusion criteria deviations
- Developed withdrawal criteria but was not withdrawn
- Received wrong treatment or incorrect dose
- Received excluded concomitant treatment

7.5**Inclusion/Exclusion Criteria**

Number and percentage of subjects who did not meet inclusion/exclusion criteria will be reported.

8.0**Patient Disposition**

The summary of subject disposition for the ITT Population will include:

- Number of subjects in the ITT population
- Number and percentage of subjects who complete the entire study
- Number and percentage of subjects who prematurely discontinue from study
- Number and percentage of subjects who remain on ADA/MTX combo after completion from study
- Number and percentage of subjects who remain ADA only after completion from study

In addition, the reasons for premature discontinuation (primary reason and all reasons) will be summarized with frequencies and percentages. Subjects with multiple reasons for premature discontinuation will be counted once in the calculation of the number and percentage of total discontinuations ("Premature Discontinuation").

9.0 Study Drug Exposure and Compliance

Summary of study drug exposure and compliance will be provided.

The study drug exposure (days) will be summarized with the mean, standard deviation, minimum, first quartile, median, third quartile and maximum, for ADA and for MTX. Study drug exposure will be summarized as follows.

Study Drug Exposure (in Days) for ADA:

- Date of last study ADA injection – Date of first study ADA injection + 14 days.

Study Drug Exposure (in Days) for MTX:

- Date of last dose of MTX – Date of first dose of MTX + 7 days.

Compliance (%), which is defined as the number of injections received divided by the number of injections planned for ADA, and as the doses received divided by the doses planned for MTX, during the subject's participation in the study (rounded to 0.1%), will be summarized separately. In addition, at each scheduled time point, the number of ADA

injections and MTX doses received and compliance will be summarized with frequencies and percentages.

When computing compliance at each scheduled time point, the denominator for each week will include all subjects in each analysis population who have not prematurely discontinued prior to the scheduled study drug injection. The date of prematurely discontinuation will be taken from vital sign dataset.

10.0 Efficacy Analysis

10.1 General Considerations

Point estimates and 95% confidence intervals (CIs) based on normal approximation will be provided for the discrete efficacy variables such as the proportion of responders to ADA/MTX. Change and percent change from baseline variables will be estimated using an appropriate estimation from a Mixed Model and statistical tests of change from baseline equal to zero will be carried out at the 0.05 significance level; 95% confidence intervals will also be provided.

Descriptive statistics will be provided. These include the number of observations, mean, and standard deviation for continuous variables and counts and percentages for discrete variables. Baseline and visit means at each scheduled visit will also be provided for change and percent change from baseline continuous variables.

Missing data will be imputed using the following methods for the efficacy analyses:

- Non-Responder Imputation (NRI): The NRI analysis will categorize any subject who has missing value at a specific visit as non-responder (or "dissatisfied" in satisfaction variables) for that visit. NRI will be the primary approach in analyses of categorical variables.
- Mixed-effect Model Repeat Measurement (MMRM): A mixed-effect model will be developed for continuous endpoint repeated measured at Baseline, Week 8, 16, and 24; controlling for time and subject ID. The fixed effects will be used to report the visit means at corresponding visits. Change and percent

change from baseline will be determined accordingly. MMRM will be the primary approach in analyses of continuous variables.

- Last Observation Carried Forward (LOCF): The LOCF analyses will use the completed evaluation from the previous visit to impute missing data at later visits. Baseline efficacy evaluations will not be carried forward. LOCF will be a sensitivity approach in analyses of continuous variables and categorical variables.

All efficacy variables will be analyzed for the ITT population overall, and separately by primary sub-optimal responders and secondary sub-optimal responders at baseline.

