Antibodies against ADA have been shown to contribute to lower treatment response in RA, PsA, CD and AS ([8](#), [14-20](#)). However, information on the relationship between TNF inhibitor serum levels, antibodies and clinical response with respect to Ps is limited ([8,14,15](#)). It is clear that subjects with Ps can develop antibodies against ADA, although the actual reported proportions with an immune response is variable, ranging from 6% following treatment discontinuation and relapse ([21](#)), 8.8% in the pivotal Phase III REVEAL clinical trial ([1](#)) and 16% and 45% in two prospective observational studies ([14,22,23](#)). The latter studies showed that trough levels of ADA were positively associated with clinical response and were significantly lower in subjects with anti-ADA antibodies ([14,22,23](#)). For example, Lecluse et al. ([22](#)) found that in 29 Ps subjects (mean PASI at baseline, 15.5; disease duration 22 years; mean number of prior systemic therapies, 4.2) who were initiated on ADA, 45% had developed anti-ADA antibodies at 24 weeks. In these subjects, titers of anti-ADA antibodies were associated with low ADA serum levels which in turn correlated with low treatment response ([22](#)). A recent study by Mahil et al. ([14](#)) confirms that antibodies against ADA contribute to a poor treatment response in Ps; after 4 weeks, ADA serum levels were significantly higher in clinical responders compared to non-responders ( $p=0.003$ ) and anti-ADA antibodies were detected in 25% of non-responders compared to none of the responders ([14](#)).

In addition to treatment failure, the presence of anti-TNF antagonist antibodies can lead to an increased risk of AEs such as acute or delayed infusion reactions which can decrease adherence to treatment regimens and lower treatment response ([15](#)).

Clinical responses to treatment failure in inflammatory diseases include dose escalation, concomitant administration of an immunosuppressant, or a switch to a different TNF antagonist ([24-27](#)). With ADA, dose escalation is accomplished by decreasing the dosing interval from two weeks to one week, and with respect to Ps, Leonardi et al. ([24](#)) found that 26.6% of subjects who initially failed ADA therapy (defined as subjects with a < PASI 50 response after 24 weeks) were PASI 75 responders 12 weeks after dose escalation. However, dose escalation is associated with increased treatment costs ([24](#)) and

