### **8.1.2 Planned Methods for Statistical Analysis**

Point estimates and 95% confidence intervals (CIs) will be provided for the discrete efficacy variables such as the proportion of responders to ADA + MTX. Changes from baseline (in PASI, PGA, DLQI and ADA serum levels) will be estimated using an appropriate estimation from a Mixed Model and statistical tests of change from baseline equal to zero will be carried out at the 0.05 significance level. Descriptive statistics will be provided as appropriate. These include the number of observations, mean, and standard deviation for continuous variables and counts and percentages for discrete variables. The analysis will be performed using SAS® (SAS Institute Inc., Cary, NC, USA).

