4.3 Sample Size

This study was planned to have a 30 month recruitment period where it was anticipated that approximately 200 subjects will be recruited. With this sample size the proportion of responders, defined as the proportion of subjects with a highly or completely satisfied response after 16 weeks of ADA/MTX therapy, based on an investigator assessment and subject self-assessment, can be estimated within $\pm 4.9\%$ with 95% confidence when the point estimate is 15%, within $\pm 6.4\%$ with 95% confidence when the point estimate is 30%, or within $\pm 6.9\%$ with 95% confidence when the point estimate is 50%. Additional accuracy estimates are provided in the table below.

Table 1. Accuracy Estimates with a Sample Size of 200 Subjects

Estimated Proportion of Responders (%)	Accuracy Estimate (%)
5	3.0
10	4.2
15	4.9
20	5.5
25	6.0
30	6.4
35	6.6
40	6.8
45	6.9
50	6.9

Note: Proportion of responders can be estimated with \pm accuracy with 95% confidence. The size of the 95% Confidence Interval would be $2 \times$ Accuracy.

Due to the enrollment plan change (enroll 50 patients or as the number of enrollment by 31 December 2016), updated accuracy estimates with a sample size of 50 subjects, about the proportion of subjects with a highly or completely satisfied response after 16 weeks of ADA/MTX therapy based on an investigator assessment and subject self-assessment, are provided in the table below.

Table 2. Accuracy Estimates with a Sample Size of 50 Subjects

Estimated Proportion of Responders (%)	Accuracy Estimate (%)
5	6.0
10	8.3
15	9.9
20	11.1
25	12.0
30	12.7
35	13.2
40	13.6
45	13.8
50	13.9

Note: Proportion of responders can be estimated with \pm accuracy with 95% confidence. The size of the 95% Confidence Interval would be $2 \times$ Accuracy.

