5.0 Analysis Populations

5.1 Definition of Analysis Populations

Intent-to-Treat (ITT) Populations

The Intent-to-Treat population will be used for all efficacy analyses, which is defined as all subjects who receive at least one dose of study ADA and at least one dose of MTX during the study.

The primary efficacy analyses will also be conducted for the following sub-populations:

- ITT Subjects who are defined as primary sub-optimal responders at baseline based on Investigator assessment.
- ITT Subjects who are defined as secondary sub-optimal responders at baseline based on Investigator assessment.

Safety Populations

The Safety Population will be used for all safety analysis, which is defined as all subjects who received at least one dose of study ADA and one dose of MTX during the study. In this study, the safety population is the same as the ITT Population.

Notations for Treatment Groups

- ADA/MTX: Subjects who received ADA and MTX as study drugs.

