10.2.2 Secondary Efficacy Variables

Secondary efficacy variables included:

- Based on investigator assessment, the proportion of subjects achieving a satisfactory response at scheduled visits other than Week 16
- Based on subject self-assessment, the proportion of subjects achieving a satisfactory response at scheduled visits other than Week 16
- Proportion of subjects achieving PASI 50/75/90/100 at all scheduled visits

- Change and percent change from baseline in PASI at all scheduled visits.
- Proportion of subjects achieving a clinical response defined as a PGA of "Clear" or "Minimal" at all scheduled visits
- Change and percent change from baseline in DLQI at all scheduled visits
- Based on investigator assessment, the proportion of subjects at each of the five categories of satisfaction at all scheduled visits
- Based on subject self-assessment, the proportion of subjects at each of the five categories of satisfaction at all scheduled visits
- Proportion of subjects achieving a DLQI score of 0 or 1 at all scheduled visits
- Change and percent change from baseline in BSA at all scheduled visits.
- Change from baseline in hs-CRP at all scheduled visits.

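### Normal-approximation confidence intervals for all responder proportions, with no fallback for small counts: a small shortfall for the overall primary endpoints, a material one for sparse counts and small sub-populations

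*SAP*

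**What the plan says.** SAP 10.1 fixes the method: "Point estimates and 95% confidence intervals (CIs) based on normal approximation will be provided for the discrete efficacy variables". The protocol leaves it open. Section 8.1.2 says only "Point estimates and 95% confidence intervals (CIs) will be provided for the discrete efficacy variables", so the SAP alone makes the choice. Neither document names an exact or score interval or a rule for zero counts, and SAP 12.0 (Special Statistical Topics) is marked not applicable.

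The sample is small. SAP 4.3 gives "updated accuracy estimates with a sample size of 50 subjects", and recruitment is to "enroll 50 patients or as the number of enrollment by" 31 December 2016, so it may end below 50. SAP 5.1 adds "The primary efficacy analyses will also be conducted for the following sub-populations", meaning primary and secondary sub-optimal responders. The end of SAP 10.1 extends that split to every efficacy variable, and SAP 10.4 analyses the PASI response endpoints by prior ADA regimen. The discrete variables include the five-category breakdown in SAP 10.2.2: "Based on investigator assessment, the proportion of subjects at each of the five categories of satisfaction at all scheduled visits", with a parallel item for the subject's rating.

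For continuous change variables SAP 10.1 plans tests: "statistical tests of change from baseline equal to zero will be carried out at the 0.05 significance level". No test or threshold is planned for proportions.

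**The concern.** The Wald interval takes its width from the observed proportion. With few responders that width is too small, the interval is forced to be symmetric, and it can extend below zero. With no responders it collapses to a single point. The method was fixed for the whole study after the target had fallen from about 200 to about 50, and it is reused in groups smaller still.

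The study is single-arm and its primary objective is to estimate a proportion. The confidence interval is therefore the only planned inference for the responder endpoints. If its stated 95% is not met, or its limits are impossible, the reader is misled about how much the study has learned. Replacing the method after seeing a 0/25 would be a post-hoc departure; naming a suitable one beforehand avoids that.

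**Working it through.** **Inputs.** Method: SAP 10.1. n=50 and planning rates of 5% to 50%: SAP 4.3, Table 2 (same as protocol Table 5). Non-responder imputation keeps the full ITT denominator (SAP 10.1), so dropout does not reduce n. Sub-population sizes are not in the documents; splits of 25/25 and 35/15 are assumed.

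**1. Reproduce Table 2.** Half-width = 1.96 × √(p(1−p)/50). At 5%: 1.96 × √(0.05 × 0.95/50) = 6.0 points. The ten rows give 6.0, 8.3, 9.9, 11.1, 12.0, 12.7, 13.2, 13.6, 13.8 and 13.9, all as printed. The planning method is therefore Wald without continuity correction. Its first row already implies 5.0 − 6.0 = −1.0% as a lower limit.

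**2. Limits at small counts.**

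| Responders | Wald (planned) | Wilson | Clopper-Pearson |
|---|---|---|---|
| 0/50 | 0 to 0% | 0 to 7.1% | 0 to 7.1% |
| 1/50 | −1.9 to 5.9% | 0.4 to 10.5% | 0.1 to 10.6% |
| 3/50 | −0.6 to 12.6% | 2.1 to 16.2% | 1.3 to 16.5% |
| 0/25 | 0 to 0% | 0 to 13.3% | 0 to 13.7% |
| 1/25 | −3.7 to 11.7% | 0.7 to 19.5% | 0.1 to 20.4% |
| 3/15 | −0.2 to 40.2% | 7.0 to 45.2% | 4.3 to 48.1% |
| 15/50 | 17.3 to 42.7% | 19.1 to 43.8% | 17.9 to 44.6% |

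The Wald lower limit is negative for 1, 2 or 3 responders at each of n=50, 35, 25 and 15.

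**3. Exact coverage.** For each n and true rate p, sum the Binomial(n, p) probabilities of every count whose interval contains p. For n=25 and p=20%, the Wald interval contains 20% only for 3 to 9 responders, and P(3 ≤ X ≤ 9) = 88.4%. The misses are lopsided: 9.8% of the time the interval lies wholly below the truth and 1.7% wholly above, against a nominal 2.5% each side.

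Wald coverage (%):

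| True rate | n=50 | n=35 | n=25 | n=15 |
|---|---|---|---|---|
| 5% | 92.0 | 83.2 | 72.1 | 53.6 |
| 10% | 87.9 | 87.1 | 91.9 | 79.2 |
| 15% | 94.1 | 90.2 | 89.9 | 89.6 |
| 20% | 93.8 | 92.5 | 88.4 | 81.5 |
| 30% | 93.5 | 91.9 | 94.9 | 94.9 |
| 50% | 93.5 | 95.9 | 95.7 | 88.2 |

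At n=50, over rates from 15% to 50% in steps of 0.01 points, the mean is 93.7% and the minimum 88.8%, a dip near 15.5%. At 2% and n=50 coverage is 63.5%.

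**4. How often the impossible limits arise.** P(negative lower limit) = P(1 ≤ X ≤ 3). For the primary endpoints at n=50 this is 4.6% at a 15% rate, 0.6% at 20% and 0.003% at 30%. P(0% to 0%) = (1−p)^n. At an assumed 5% rate this is 7.7% (n=50), 16.6% (n=35), 27.7% (n=25) and 46.3% (n=15).

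**5. Are small counts realistic?** Five satisfaction categories sum to 100%, so at least one share is at or below 20%. In a group of 15 the average category holds 15/5 = 3 subjects. For PASI 90/100, PGA clear or minimal, and DLQI 0 or 1, the documents give no expected rates. The nearest figure, in the protocol introduction, is that "26.6% of subjects who initially failed ADA therapy" reached PASI 75 after dose escalation. That is a different regimen, so indicative only, but PASI 90 and 100 cannot exceed PASI 75.

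**6. Alternatives over rates of 2% to 50%.** Wilson: mean 95.2% to 95.4% across the four sizes, minimum 91.6% (n=50) and 89.4% (n=25 and 15). Clopper-Pearson: minimum 95.1% at n=50, 25 and 15.

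**The case against.** No decision depends on these intervals. There is no null rate, success threshold or comparison for proportions, and the protocol itself calls the study qualitative. For the overall primary endpoints the change is slight: at 15/50 the limits move by one to two points, and at a true rate of 50% Wilson and Wald both cover 93.5%. The 88.8% minimum is a single dip; the 93.7% mean is the fairer summary. All of this stands, and it limits the weight of the point.

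The sub-population sizes and the low endpoint rates are assumptions. This also stands. With 25 subjects and a rate of 30% or 50%, Wald covers 94.9% and 95.7%. The category argument forces a share of 20% or less, and at n=50 Wald still covers 93.8% at that rate. The sub-population shortfall is therefore material mainly below about 30%, or when one group is clearly smaller than 25.

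Wilson is not better everywhere. At a 30% rate it covers 92.3% against 94.9% for Wald at n=25, and 91.5% against 94.9% at n=15. This is a reason to consider Clopper-Pearson, not to keep Wald.

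Counts and percentages will be shown, so a reader can spot a sparse cell and recompute. That reduces the harm but does not make a negative or zero-width interval fit to report. Truncating at zero would hide the impossible limit without restoring coverage.

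**Conclusion.** The concern holds and should be acted on; confidence is high. SAP 10.1 prescribes a single interval method that is adequate for the overall primary endpoints at planning rates of 15% to 50% (about 1 to 1.5 points below nominal at 15%, 30% and 50%) and inadequate for sparse counts. Two results need no assumption about sub-population size or endpoint rates: the limits printed for zero to three responders out of 50, and coverage of 87.9% at the 10% rate in the SAP's own Table 2. The figures for n=35, 25 and 15 rest on the assumed splits, and those for rates of 2% and 5% in the secondary endpoints rest on assumed low rates. The consequence is misstated precision in the report. No type I error decision is affected.

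**What to change.** In SAP 10.1, replace the normal-approximation phrase with one named method for all binary and categorical proportions, overall and in both sub-populations. Wilson score suits if average coverage near 95% is enough; Clopper-Pearson suits if at least 95% is to be guaranteed. Choose one before SAP sign-off.

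The cost is one phrase and one program option. Intervals become asymmetric and, if exact, slightly wider (15/50: 17.9 to 44.6% instead of 17.3 to 42.7%). Protocol 8.1.2 names no method, so no amendment is needed.

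A secondary step is to restate SAP Table 2 as lower and upper limits. With Wilson at n=50: 5% gives 1.6 to 14.9%, 15% gives 7.6 to 27.4%, 30% gives 19.1 to 43.8%, and 50% gives 36.6 to 63.4%. This would make the SAP table differ from protocol Table 5, whose change would need an amendment with ethics committee approval (protocol 9.1). It can be left out without weakening the main fix; protocol Table 5 should be aligned only if an amendment is made for other reasons.

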#### **5.2.3.4                   Rescue Therapy**

There are no rescue therapy protocols for this study.

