**5.4 Removal of Subjects from Therapy or Assessment****5.4.1 Discontinuation of Individual Subjects**

A subject may withdraw from the study at any time. The Investigator may discontinue any subject's participation for any reason, including an AE, safety concerns or failure to comply with the protocol.

Subjects will be withdrawn from the study immediately if any one of the following occurs:

- Clinically significant abnormal laboratory result(s) or AEs, as determined by the Investigator in consultation with the AbbVie Study-Designated Physician.
- The Investigator believes it is in the best interest of the subject.
- The subject requests withdrawal from the study.
- Inclusion and exclusion criteria violation was noted after the subject started study drugs, when continuation of the study drugs would place the subject at risk, as determined by the AbbVie Medical Monitor (see Section [7.0](#)).
- Introduction of prohibited medications or dosages when continuation of the study drug would place the subject at risk as determined by the AbbVie Study-Designated Physician.
- Subject is non-compliant with TB prophylaxis.
- The subject becomes pregnant while on study medication.
- Subject has dysplasia of the gastrointestinal tract or a malignancy, except for localized non-melanoma skin cancer. Discontinuation for carcinoma in-situ of the cervix is at the discretion of the Investigator.
- Subject is diagnosed with lupus-like syndrome, multiple sclerosis or demyelinating disease.
- Subject is significantly non-compliant with study procedures which would put the subject at risk for continued participation in the trial, as determined by the Investigator, in consultation with the AbbVie Medical Monitor and the Investigator.

If, during the course of study drugs administration, the subject prematurely discontinues either ADA or MTX, the procedures outlined for the Termination Visit must be completed within 2 weeks of the last dose of either drug, and preferably prior to the initiation of

---

another therapy. However, these procedures should not interfere with the initiation of any new treatments or therapeutic modalities that the Investigator feels are necessary to treat the subject's condition. Following discontinuation of ADA or MTX, the subject will be treated in accordance with the Investigator's best clinical judgment.

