#### **6.1.7      Toxicity Management**

Subjects who develop a new infection while undergoing treatment with ADA and MTX should be monitored closely. Administration of study ADA injections and/or oral MTX should be interrupted if a subject develops an infection requiring intravenous (IV) anti-infective treatment or if an infection meets the definition of "serious" (see Section [6.0](#) for definitions). Study medication may be restarted once the Investigator determines that the

infection has been successfully treated. Otherwise prohibited concomitant medications may be given if medically necessary. Prior to any prohibited medication use, every attempt should be made to contact the AbbVie Medical Monitor for direction on re-introduction of ADA and MTX therapy after prohibited medication administration; however, these communications should not delay the administration of any necessary medication(s), study-prohibited or otherwise, to the subject.

If the subject must undergo elective surgery, the study ADA injections and oral MTX must be interrupted 2 weeks prior to the surgery. If the subject must undergo emergency surgery, the study ADA injections and oral MTX must be interrupted at the time of the surgery. ADA and oral MTX can recommence at least 2 weeks after surgery once the physician has examined the surgical site and determined that it has healed and there is no sign of infection. If any subject needs to skip more than two ADA doses or two weekly doses of MTX (consecutive or intermittent) over the course of the study, even if for the situations described above, further follow-up on the subject's study participation should be discussed with the AbbVie Study designated Physician.

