### **8.1.1 Analysis Population**

The intent-to-treat (ITT) population will be used in the assessment of treatment satisfaction and in the evaluations of ADA + MTX efficacy. The ITT population is defined as:

- All subjects who received at least one dose of ADA and one dose of MTX.

A per protocol population will not be defined for this qualitative study.

The safety population is defined as all subjects who received at least one dose of ADA and one dose of MTX and will be used to evaluate safety of ADA + MTX.

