10.2 Efficacy Variables

10.2.1 Primary Efficacy Variable

The primary efficacy endpoints will be:

- Based on investigator assessment, the proportion of subjects achieving a satisfactory response at Week 16 (satisfactory response is defined as highly or completely satisfied with therapy based on responses to the satisfaction questionnaire).
- Based on subject self-assessment, the proportion of subjects achieving a satisfactory response at Week 16 (satisfactory response defined as highly or completely satisfied with therapy based on responses to the satisfaction questionnaire).

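### No planned analysis deals with Week 16 ratings made after a subject starts prohibited psoriasis therapy, so such subjects can count as ADA+MTX responders

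*SAP*

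**What the plan says.** **Endpoint and missing data.** The two primary endpoints are the shares of ITT subjects rated highly or completely satisfied, by the investigator and by the subject. SAP 10.2.1 words the first as "Based on investigator assessment, the proportion of subjects achieving a satisfactory response at Week 16"; neither depends on what else the subject is taking. SAP 10.1 then states: "The NRI analysis will categorize any subject who has missing value at a specific visit as non-responder". The LOCF sensitivity analysis also acts only on missing values. Protocol 8.1.1 adds: "A per protocol population will not be defined for this qualitative study".

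**Added therapy.** Protocol 5.2.3.3 lists prohibited treatments, and 5.2.3.4 says "There are no rescue therapy protocols for this study". Protocol 5.4.1 requires immediate withdrawal for "Introduction of prohibited medications or dosages when continuation of the study drug would place the subject at risk". For other cases it gives discretion: "The Investigator may discontinue any subject's participation for any reason, including an AE, safety concerns or failure to comply with the protocol".

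**Early stoppers.** Under protocol 5.4.1 the termination visit is due within two weeks of the last dose of either drug. Holding it before new therapy is only a preference, and it must not delay that therapy. Protocol Table 1 schedules both satisfaction questionnaires at Week 24/ET. SAP Table 4 assigns assessments on Rx Days 86 to 141 to Week 16.

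**Reporting.** SAP 7.4 tabulates subjects who received excluded concomitant treatment. SAP 7.3 counts a drug started during treatment as concomitant, "but not after the last study ADA dose date during the study".

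**The concern.** The objective is response to the ADA/MTX combination. The questionnaires (protocol Appendix C) ask about the subject's current regimen or current psoriasis treatment. A subject who has added another psoriasis therapy is rating that therapy too, yet a favourable answer is credited to ADA+MTX.

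There is no control arm in which similar use could be seen, so the Week 16 proportion is the main result. A shift from added therapy is a bias: the confidence interval does not widen to reflect it, and no planned analysis would show how far the estimate depends on it. Protocol 7.0 and SAP 7.4 show that the sponsor foresees the event. What is missing is the link from that event to the response analysis.

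**Working it through.** **1. The plan's own precision figure.** Inputs: n = 50 and a 95% interval by normal approximation (SAP 4.3 and 10.1). Half-width = 1.96 × √(p(1−p)/n).

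- p = 15%: 1.96 × √(0.15 × 0.85/50) = 9.9 points
- p = 30%: 1.96 × √(0.30 × 0.70/50) = 12.7 points
- p = 50%: 1.96 × √(0.50 × 0.50/50) = 13.9 points

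These match SAP Table 2 and protocol Table 5.

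**2. Effect of affected responders.** One subject is 1/50 = 2.0 points. Suppose k observed responders owe their rating to added therapy. The rate without them is (x − k)/50, with the same interval formula. The values of k are assumed.

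| k recoded | From 15/50 = 30.0% (17.3 to 42.7) | From 25/50 = 50.0% (36.1 to 63.9) |
|---|---|---|
| 1 | 28.0% (15.6 to 40.4) | 48.0% (34.2 to 61.8) |
| 2 | 26.0% (13.8 to 38.2) | 46.0% (32.2 to 59.8) |
| 3 | 24.0% (12.2 to 35.8) | 44.0% (30.2 to 57.8) |
| 5 | 20.0% (8.9 to 31.1) | 40.0% (26.4 to 53.6) |

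Enrolment may close below 50 (SAP 4.3), and the primary analyses are repeated in primary and secondary sub-optimal responders. With a smaller denominator each subject weighs more.

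**3. Can an early stopper's rating land in Week 16?** Assume both drugs start on the same day. The nominal Rx day of a dose is 7 × week + 1, and the termination visit falls up to 14 days later.

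- Last ADA dose at Week 10: Day 71, visit by Day 85. This is in the Week 8 window.
- Last ADA dose at Week 12: Day 85, visit by Day 99. A visit from Day 86 is in the Week 16 window.
- Last ADA dose at Week 14: Day 99, visit by Day 113. This is in the Week 16 window.

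So a termination visit on Days 86 to 113 supplies a non-missing Week 16 rating, and NRI does not apply even if new therapy has begun. A drug started after the last ADA dose is also outside the SAP 7.3 definition.

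**4. What the SAP 7.3 cut-off does in completers.** The last ADA dose is at Week 22, Day 7 × 22 + 1 = 155. The Week 16 window closes on Day 141, so any drug started before a completer's Week 16 assessment falls within the definition. The gap runs from Day 155 to the nominal Week 24 visit on Day 169, which is 14 days, although MTX continues to Week 23.

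**The case against.** The study describes itself as real-world, uses an ITT set and deliberately defines no per-protocol set. Analysing ratings as observed, whatever else was taken, is a recognised choice. That stands as a defence of the as-observed result as primary. It does not explain why the choice is unstated or why nothing tests it, given an objective about the combination.

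Four stronger readings are tempting, and the documents do not support them:

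- *Subjects given prohibited therapy stay in the study.* Those at risk must be withdrawn, and the investigator may discontinue others. The accurate statement is that withdrawal is not mandatory without risk.
- *The report would hide the problem.* SAP 7.4 counts excluded treatment, with no cut-off at the last ADA dose, and protocol 7.0 makes it a reportable deviation. The table shells are in a separate document. What is absent is the connection to response.
- *The SAP 7.3 cut-off contaminates Week 16.* In completers it cannot. It limits detection for Week 24 and for early stoppers, and does not itself cause bias.
- *The protocol opens a route to extra psoriasis treatment.* The sentence "Otherwise prohibited concomitant medications may be given if medically necessary" is in 6.1.7, Toxicity Management, in text on infections, and asks sites to try to reach the Medical Monitor. It shows that a subject may receive a prohibited drug and resume study drug, and no more.

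It is also fair to object that making every later visit a failure would over-correct: a short corticosteroid course given for another reason would then count against the combination. This argues for a sensitivity analysis rather than a new primary rule.

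**Conclusion.** The concern holds as a gap in the analysis plan. Two groups can count as ADA+MTX responders at Week 16 after starting prohibited psoriasis therapy: subjects who are not withdrawn because no risk is judged to exist, and early stoppers whose termination visit falls in the Week 16 window. Neither NRI, LOCF nor any analysis set addresses them.

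The size cannot be derived from the documents. Each affected responder adds 2 points at n = 50. The range of 2 to 10 points assumes 1 to 5 such subjects, each of whom would otherwise have been a non-responder. At the top of that range the shift approaches the planned half-width of 12.7 to 13.9 points at response rates of 30% to 50%; with one subject it is minor. Overstatement is the expected direction, not a certain one. A reader might infer that added therapy can only raise the rate, but a prohibited drug may be given for another reason and leave the rating unchanged, and a subject who needs more treatment may still be rated as dissatisfied.

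This is a change that should be made. It does not invalidate the primary analysis.

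**What to change.** 1. **SAP 10.1.** Add a pre-specified sensitivity analysis of both primary endpoints. Count as a non-responder any subject whose Week 16 assessment follows the start of a therapy given for psoriasis, or of a systemic corticosteroid, that is prohibited during the study under protocol 5.2.3.3. Show the as-observed result alongside. If added therapy does not worsen ratings, the two results bracket the answer. Flag the drugs by name, indication and start date before database lock. Several entries in 5.2.3.3 combine a ban during the study with an interval before baseline, so the SAP must state how it reads that list. This implies no view on what should be prohibited or when a subject should be withdrawn.
2. **SAP 7.3.** End the concomitant medication period at the later of the last dose of either study drug and the last efficacy visit. This matters for Week 24 and for early stoppers.

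**Cost.** Medications are already recorded through Week 24/ET (protocol 5.2.3 and Table 1). The work is one derived flag, a short review of drug and indication, and one extra row for each primary endpoint. The sensitivity rate may look slightly lower, and a short course given for another reason may be counted conservatively.
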